10. STATISTICAL CONSIDERATIONS

10a. Accrual: Based on previous years' treatment records, we anticipate that there will be about 40-50 eligible patients per month across the multiple participating academic and community centers. The accrual rate of this study is expected to be about 22 patients per month. We expect conservatively (based on survey data) that 75% of the eligible patients (after confirmation of the need for radiation therapy) are willing to be randomized to either the long-course or short-course treatment. The accrual will be open until 400 patients are enrolled. Randomization will be stratified by treatment center and age of the patient (<45 vs. ≥45). We expect the proportion of patients in the younger cohort of the study sample to be 40%. The anticipated length of the accrual period is 21-27 months.

10b. Statistical analysis plan for patient-reported quality of life outcomes and power considerations

Quality of life (QoL) measurement and the primary endpoint: We will use an array of instruments to rigorously assess quality of life among study participants, such as the FACT-B scores, satisfaction with breast surgery outcomes (BREAST-Q), Lymph-ICF, and financial burden. We will record and report all reasons for dropout and which outcomes were not reported, and include this data in our final reports. FACT-B (version 4) specifically measures quality of life in breast cancer patients and includes modules for assessing physical well-being, emotional well-being, social well-being, functional well-being and a 2-item question characterizing a breast cancer patient's relationship with her physician. QoL will be assessed at baseline, 6 months, 12

months and 18 months. This data will allow peer reviewers and readers of our publications to assess the validity of our study.

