To determine the primary endpoint among those measurement scales, we surveyed patients who had undergone radiation therapy after mastectomy and immediate reconstruction and found that the majority of chose **the Physical Well-Being (PWB) subscale of the FACT-B (version 4) to be the most important element of their quality of life, regardless of age** (data not shown, manuscript in preparation). Based on this result, we selected the FACT-B PWB score as the primary endpoint of this study. To adjust for QoL at baseline, we will compare change in PWB score (relative to each patient's pre-radiation score) between the short and long-course treatment groups, instead of comparing PWB scores between the two groups.

Statistical analysis of the primary endpoint and power: As per the intention-to treat principle, the primary analysis population will be all women who are randomly assigned to receive either short-course or long-course (conventional) radiation therapy. The secondary analysis population will be the per-protocol cohort. We hypothesize that the short-course radiation therapy will lead to improved PWB scores compared to the conventional long-course treatment. To confirm this hypothesis, we will use Analysis of Covariance (ANCOVA) models. **Change in the FACT-B PWB subscale (7 items) score at 6 months relative to baseline** will be the response variable, and the intervention group indicator (long-course versus short-course radiation therapy) and age group (below 45 vs. 45 or above) will be included in the ANCOVA model as independent variables. Using change in the PWB score relative to baseline will give us a more normal distribution of outcomes, versus using the score itself. **The age threshold of 45 years was selected by our patient advocates.**

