Based on our patient survey data, we anticipate that the mean post-conventional (long-course) PWB score to be 19.0 for the younger patient group and 24.0 for the older group, and that the standard deviation (SD) is 6.0 for each. We also expect the correlation coefficient between the baseline and 6-month value to be 0.65-0.7, thus the SD of change from baseline to 6 months will be 3.6 to 4.2. **“Table: Expected PWB subscale scores at 6 months by treatment arm”** shows the expected treatment effect in each age group, based on our preliminary data and studies of short-course therapy in other breast cancer settings. The effect of short-course radiation on quality of life outcomes in these other breast cancer settings (breast-conserving surgery or mastectomy without reconstruction) are likely underestimates for our study given the relatively poor outcomes of long-course radiation after mastectomy with reconstruction, rendering our treatment effect expectation to be conservative. The PWB subscale of FACT-B has been documented to have sensitivity to change in quality of life measurement,³⁷ and change in PWB has been used to study other breast cancer interventions.^{47,48} A change in PWB score of greater than or equal to 2 has been defined as clinically meaningful in a multicenter radiation technique study in lung cancer patients.⁴⁹ In a study of 41 patients with gynecologic cancer, radiation therapy led to a mean decline of 3.1 points in PWB score, and was associated with radiation treatment technique.⁵⁰ With expected data from a total of 400 patients (200 for each arm), the study will have sufficient power, at a two-sided 0.05 alpha level, to detect a marginal treatment difference of 2.8 in PWB scores. If the SD of change from baseline to 6 months is 4.0, the study's power will be 93%. We will also perform the test for interaction between age group and intervention group on the outcome to **investigate the heterogeneity of treatment effect (section**

10e).

Table: Expected PWB subscale scores at 6 months by treatment arm			
	Younger patients (under 45)	Older patients (45 and above)	Marginal score
Short-course (hypofractionation) treatment	23.0	26.0	24.8
Long-course (conventional) treatment	19.0	24.0	22.0
Difference in differences from baseline score	4.0	2.0	2.8

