Under the same setting as shown described above, “**Table: N=400 randomized patients, $\alpha=0.05$** ” reveals the power to detect an age interaction will be 59%-89%. These are conservative estimates for the 6-month change in PWB, given that patients in our survey were interviewed between 6 and 24 months (data not shown, manuscript in preparation), and there may be some recovery in physical symptoms with time.

Table: N=400 randomized patients, $\alpha=0.05$.				
PWB score Δ		SD of Δ	Power	
Younger patients	Older patients		Main analysis	Interaction
4.0	2.0	3.5	>0.99	0.80
4.0	2.0	4.0	>0.99	0.69
4.0	2.0	4.5	>0.99	0.59

Strategy for handling missing data: Given the patient incentives, short time required to complete surveys, and enthusiasm voiced by the patients we surveyed, we expect that the dropout fraction from the study at 6 months will be at most 5% and that the dropout mechanism would be mostly random. In a primary analysis, we will exclude those who dropout from the study or who do not have data at 6 months. However, because a random missing mechanism assumption is not verifiable empirically, we will use several methods to handle missing observations to confirm the stability of the findings from the primary analysis. Specifically, we will perform the following: (1) last observation carried forward (LOCF), (2) mean value imputation, (3) worst-case and (4) best-case imputation. We will also conduct (5) multiple imputation⁵¹. For multiple imputation, we will create 10 complete datasets, imputing the missing values using chained equations. We will perform the analysis with the 10 complete datasets and integrate the results with Rubin’s method of imputation.⁵¹ For another approach, we will analyze this data according to (6) the methods described in Schluchter and in Schluchter, Greene and Beck.^{52,53} These methods take into account the possibility of informative “missingness” by jointly modeling the longitudinal responses (here, QoL scores) and the time to dropout.

Other QoL analysis: In secondary analyses, we will use generalized estimating equation (i.e., marginal modeling) and random-effects models to analyze longitudinal data⁵⁴ (i.e., baseline, 6 months, 12 months and 18 months) for the FACT-B total score (37 items) and each subscale as well as the primary endpoint (FACT-B PWB subscale).

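### The primary ANCOVA on 6-month PWB change leaves out baseline PWB; adding it costs one degree of freedom and can only help precision, by an amount that depends on a baseline SD the plan does not give

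*Combined protocol and SAP*

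**What the plan says.** Section 10b of the combined protocol and SAP states how baseline is to be handled: "To adjust for QoL at baseline, we will compare change in PWB score", relative to each patient's pre-radiation score. The response in the primary analysis is the change at 6 months. The intervention indicator "and age group (below 45 vs. 45 or above) will be included in the ANCOVA model as independent variables". No other term is listed.

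The baseline value will be available: "QoL will be assessed at baseline, 6 months" and later. The planning inputs are a post-treatment mean ("we anticipate that the mean post-conventional (long-course) PWB score to be 19.0" for younger patients, 24.0 for older ones), a spread ("and that the standard deviation (SD) is 6.0 for each"), and a correlation: "We also expect the correlation coefficient between the baseline and 6-month value to be 0.65-0.7". From these the plan concludes "thus the SD of change from baseline to 6 months will be 3.6 to 4.2". No SD is given for the baseline score. The survey behind these inputs was taken after treatment: "patients in our survey were interviewed between 6 and 24 months".

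The GEE and random-effects models in section 10b use all time points, baseline included, but they are secondary. Sections 5.3 and 10a stratify the randomization by treatment center and age group. Of these two factors, only age group is in the primary model.

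**The concern.** Subtracting baseline is the same as including it with a slope fixed at 1. When the true within-group slope is lower, the change score over-corrects: part of the baseline noise is put back with the opposite sign. This has three effects.

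- The confidence interval for the primary estimate is wider than it needs to be.
- A chance difference between arms in baseline PWB moves the estimate in the opposite direction, which is what the adjustment is meant to prevent.
- The age-by-arm test, where power is limited, loses some of it.

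The validity of the primary test and its power for the assumed effect are not at stake.

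**Working it through.** **Inputs.** From section 10b: 6-month SD 6.0 in each age group, r = 0.65-0.70, 200 per arm, effect 2.8 overall (4.0 younger, 2.0 older), two-sided alpha 0.05. From section 10a: 40% under 45, so 80 younger and 120 older patients per arm. Assumed: SD and r apply within age group and are the same in both arms. Also assumed is k = baseline SD / 6-month SD, taken from 0.8 to 1.2 because the documents give no baseline SD.

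**The plan's own figures.** The interaction SE is SD × √(2/80 + 2/120) = 0.204 × SD. For a difference of 2.0 and SDs of 3.5, 4.0 and 4.5, power is 0.80, 0.69 and 0.59, as in the plan's table. For the main effect at SD 4.0, 2.8 / (4.0 × √(2/200)) = 7.0 standard errors, so power exceeds 0.99. This agrees with the table but not with the 93% in the text, which is a separate matter.

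**Formulas.**
- Variance of change: 36(1 + k² − 2rk)
- Residual variance with baseline in the model: 36(1 − r²), that is SD 4.56 at r = 0.65 and 4.28 at r = 0.70
- Fraction removed: (k − r)² / (1 + k² − 2rk), which is never negative and is zero only at k = r
- Slope implied by the plan: r/k
- 95% CI half-width: 1.96 × SD × √(2/200)

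**Example, k = 1.** The variance of change is 36 × 2(1 − r), so the SD is 5.02 (r = 0.65) or 4.65 (r = 0.70). The fraction removed is (1 − r)/2 = 17.5% or 15.0%. The half-width falls from 0.98 to 0.89, or from 0.91 to 0.84. The equivalent sample size is 400 × 5.02²/4.56² ≈ 485, or 471 at r = 0.70.

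**Results over k.** Each cell gives r = 0.65, then r = 0.70.

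| k | SD of change | Variance removed | Equivalent N | Interaction power, without → with baseline |
|---|---|---|---|---|
| 0.8 | 4.65; 4.33 | 3.8%; 1.9% | 416; 408 | 0.56 → 0.57; 0.62 → 0.63 |
| 0.9 | 4.80; 4.45 | 9.8%; 7.3% | 443; 431 | 0.53 → 0.57; 0.60 → 0.63 |
| 1.0 | 5.02; 4.65 | 17.5%; 15.0% | 485; 471 | 0.50 → 0.57; 0.56 → 0.63 |
| 1.1 | 5.30; 4.91 | 26.0%; 23.9% | 540; 525 | 0.46 → 0.57; 0.51 → 0.63 |
| 1.2 | 5.63; 5.23 | 34.4%; 32.9% | 610; 596 | 0.41 → 0.57; 0.47 → 0.63 |

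The half-width falls by 0.01-0.02 points at k = 0.8 and by 0.19-0.21 at k = 1.2. The lowest main-effect power anywhere in the grid is 0.9987 (change score, k = 1.2, r = 0.65).

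**Chance imbalance.** Each point of baseline difference between arms shifts the change-score estimate by 1 − r/k: 0.30-0.35 at k = 1, 0.13-0.19 at k = 0.8 and 0.42-0.46 at k = 1.2. The baseline arm difference has SE 6k√(2/200) = 0.6k. At its 95% limit the shift is 1.96 × 0.6 × (k − r): 0.35-0.41 points at k = 1, 0.12-0.18 at k = 0.8 and 0.59-0.65 at k = 1.2.

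**Second input set.** The stated SD of change (3.6-4.2) cannot be reconciled with SD 6.0 and r 0.65-0.70. Over any baseline SD, the smallest possible value is 6√(1 − r²) = 4.28-4.56. If SD 6.0 and the stated SD of change are kept and r is left free, r = (1 + k² − (SD of change/6)²)/(2k). At k = 1 this gives r = 0.82 for 3.6 and 0.755 for 4.2. The variance removed is then 0-1.4% at k = 0.8, 2.5-5.7% at 0.9, 9-12% at 1 and 31% at 1.2. At k = 1 the half-width falls by 0.03-0.05 points and interaction power rises by 4-6 percentage points.

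**Simulation.** In 4,000 simulated trials per setting (N = 400, effect 2.8), both estimators averaged 2.79-2.80. At k = 1 the change-score estimate moved by −0.31 to −0.35 per point of baseline imbalance. With baseline in the model the movement was −0.03 to +0.01.

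**The case against.** The strongest reply is that nothing in the primary conclusion turns on this. The planned test is valid, power for 2.8 points exceeds 0.99 in every case, and a half-width gain of 0.07-0.09 points is small beside the 2 points that section 10b cites as clinically meaningful. The interaction test that gains most is treated as hypothesis-generating in section 10e. All of that stands, and it is why the point is graded as an improvement.

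The change score was also a deliberate choice, partly because the plan expects change to be closer to normally distributed. The remedy respects this, since change remains the response.

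The size of the gain is uncertain. The range for k is assumed, and under the second input set the gain at k = 0.8 is close to nothing. That also stands. The direction does not depend on it, because the fraction removed cannot be negative.

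Section 5.2 lets the baseline questionnaire be completed at any time between consent and the start of radiation, which can be up to 4 months after randomization. A baseline score could therefore be given after the arm is known, and an imbalance would then not be purely chance. This weakness affects the planned change score equally, so it does not favor the planned model. It is a reason to obtain baseline before randomization.

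Finally, a random intercept for center turns the analysis into a mixed model, and no gain has been quantified for it. That is fair. The baseline recommendation does not depend on it.

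**Conclusion.** The point holds. The primary model omits a baseline score that is already collected and correlated with the outcome, and nothing elsewhere in the plan adds it to that model. On the plan's SD of 6.0 and r of 0.65-0.70, the residual variance removed is 15-17.5% if baseline and 6-month SDs are equal, and about 2% to 34% for SD ratios of 0.8 to 1.2. On the stated SD of change it is 0% to 31%. The direction is certain, apart from the loss of one degree of freedom. The size is not, because the baseline SD is missing and the stated inputs conflict. The benefit is a narrower interval, protection against chance baseline imbalance and some power for the age interaction. The change should be made, but the trial's primary conclusion does not hang on it.

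**What to change.** Before any unblinded analysis, specify the primary model as: 6-month PWB change = arm + baseline PWB (continuous) + age group. Use the same model plus arm × age for the interaction test. With baseline in the model, the arm estimate is identical whether the response is the change or the 6-month score, so the stated endpoint is unchanged.

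The cost is one SAP sentence and one degree of freedom. No new data are needed, and no further patient is excluded, because a patient without a baseline score already has no change score.

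Two accompanying points:

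- To align with the stratified randomization, add treatment center as a random intercept. This needs one more sentence, which should name the estimation method and the fallback if the center variance is estimated at zero. It needs no pooling rule for small centers.
- Ask that the baseline questionnaire be completed before randomization where possible. Section 5.2 already recommends completion immediately after consent.

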5.3 Stratification Factors and Treatment Assignment

400 patients will be randomized 1:1 into either Arm 1 (short-course PMRT) or Arm 2 (long-course PMRT).

Randomization will be stratified by treatment center and age of the patient (<45 vs. ≥45).

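### The primary ANCOVA omits treatment center, a stratification factor; if PWB change differs by center, the interval is somewhat too wide and the test conservative

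*Combined protocol and SAP*

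**What the plan says.** Section 10a states: "Randomization will be stratified by treatment center and age of the patient", with age cut at 45. Section 5.3 says the same and sets 1:1 allocation of 400 patients.

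Section 10b defines the primary response as "Change in the FACT-B PWB subscale (7 items) score at 6 months relative to baseline". The model terms are the intervention indicator and age group, which "will be included in the ANCOVA model as independent variables". Center is not among them.

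Center is also absent from the rest of Section 10. The random-effects models in 10b are for the repeated QoL measurements and do not mention center. The missing-data sensitivity analyses do not add it, and the table of heterogeneity attributes in 10e does not list it. No reason for leaving it out is given.

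**The concern.** The plan carries one of its two stratification factors into the primary model and drops the other without comment. Stratified allocation holds the arms close to balance within each center, so differences between centers largely cancel out of the treatment estimate. A model without center still counts those differences as residual error. Its standard error then describes a less precise design than the one that was run.

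A center effect is plausible from the protocol itself. Section 2.1 plans both academic and community sites. Sections 6.2 and 6.4 leave bolus, nodal targets, volume delineation and lung and heart limits to the treating physician or institution. At stake are the width of the primary interval, the actual level of the primary test, and some power for the age-by-arm interaction, which is the weakest test in the 10b power table.

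**Working it through.** **Inputs from the documents.** 200 patients per arm, two-sided alpha 0.05, marginal difference 2.8, SD of change 4.0, 40% of patients under 45, at most 5% dropout at 6 months (about 380 analysed).

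**Inputs assumed.** Between-center share of the variance of PWB change (ICC) 0, 0.02, 0.05 and 0.10; 10, 16 or 30 centers of unequal size; permuted blocks of 4 within center by age group. The documents give none of these.

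**Step 1, the plan's own power.** SE = 4.0 × √(2/200) = 0.40. The difference is 2.8/0.40 = 7.0 standard errors, and 7.0 − 1.96 = 5.04, so power exceeds 0.9999. This agrees with the >0.99 in the 10b table. It does not agree with the text, "If the SD of change from baseline to 6 months is 4.0, the study's power will be 93"%: at 200 per arm that figure would need an SD of about 8.1 or a difference of about 1.37. That inconsistency is a separate matter. Power for a difference of 2.8 is still 0.997 at an SD of 6.0.

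**Step 2, large-sample effect of omitting center.** With center in the model the residual SD is 4.0 × √(1 − ICC). The ratio of widths (omitted/included) is 1/√(1 − ICC). The true level of the test without center is 2 × [1 − Φ(1.96/√(1 − ICC))].

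| ICC | 95% half-width, center omitted | center included | ratio | true alpha, center omitted |
|---|---|---|---|---|
| 0 | 0.784 | 0.784 | 1.000 | 0.050 |
| 0.02 | 0.784 | 0.776 | 1.010 | 0.048 |
| 0.05 | 0.784 | 0.764 | 1.026 | 0.044 |
| 0.10 | 0.784 | 0.744 | 1.054 | 0.039 |

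**Step 3, simulation.** The formula ignores the degrees of freedom spent on center and the incomplete blocks in small strata. A simulation with n = 380, SD 4.0 and 3,000 runs per cell compared the model with arm and age group against the same model with fixed center effects. Width ratios (omitted/included):

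| ICC | 10 centers | 16 centers | 30 centers |
|---|---|---|---|
| 0 | 0.999 | 0.997 | 0.991 |
| 0.02 | 1.008 | 1.005 | 0.999 |
| 0.05 | 1.021 | 1.021 | 1.014 |
| 0.10 | 1.044 | 1.049 | 1.041 |

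Without center, the simulated type I error was 0.043 to 0.045 at ICC 0.05 and 0.041 to 0.044 at ICC 0.10. The Monte Carlo standard error is about √(0.05 × 0.95/3000) = 0.004, so these values agree with Step 2 within simulation error. Simulated power at a difference of 2.8 was 1.00 with and without center (16 centers, ICC 0.05, 1,000 runs).

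**Step 4, the interaction test.** With 80 younger and 120 older patients per arm, SE = 4.0 × √(2/80 + 2/120) = 0.816. For age-specific effects of 4.0 and 2.0 the contrast is 2.0, and power is Φ(2.0/0.816 − 1.96) = 0.69, as in the 10b table. SDs of 3.5 and 4.5 likewise reproduce its 0.80 and 0.59.

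- Center included: SE is 0.816 × √0.95 = 0.796 at ICC 0.05 (power 0.71) and 0.816 × √0.90 = 0.775 at ICC 0.10 (power 0.73).
- Center omitted: the estimate has the same true spread but is judged against 1.96 × 0.816 = 1.60. Power is Φ((2.0 − 1.60)/0.796) = 0.69 at ICC 0.05 and Φ((2.0 − 1.60)/0.775) = 0.70 at ICC 0.10.

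The gain is about 0.02 to 0.03, before any loss of degrees of freedom.

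**The case against.** The strongest objection is that the harm is conditional and nothing in the documents shows that the condition is met. The response is a change from each patient's own pre-radiation score, so persistent center differences in PWB level cancel; only differences in change matter, and no figure for these is given. The plan does adjust for age, the factor it expects to be prognostic (19.0 against 24.0 points under conventional treatment). Center may have many levels and sparse strata, so leaving it out is a defensible simplification. With no center effect and 30 centers, fixed effects would make the interval about 1% wider. The interaction test belongs to a heterogeneity analysis that 10e describes as hypothesis-generating. The missing baseline PWB covariate probably costs more: on the plan's correlations of 0.65 to 0.70, √[2(1 − r)]/√(1 − r²) = 1.10 to 1.08, or about 8% to 10% of interval width.

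All of this stands, and it limits the point to a small one. It does not remove it: the sponsor stratified by center, the model leaves center out, and no reason is stated.

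A reader might infer more: that the primary interval certainly is too wide, or that the primary test is invalid or short of power. The documents support neither. The first needs a between-center variance that they do not give. The second is contradicted by the direction of the error, which is conservative, and by power above 0.99.

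**Conclusion.** The point holds in conditional form. Center is a randomization factor and is missing from the primary model. If PWB change varies by center, the reported standard error is too large, the interval too wide and the test conservative.

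Over the assumed ICCs and numbers of centers, the effect on interval width runs from about -1% to +5%. At ICC 0.05 the half-width would be 0.764 instead of 0.784 points, a difference of 0.02 against an expected effect of 2.8. The treatment estimate is not biased, because allocation is randomized 1:1 within strata. No conclusion of the main analysis is at risk under the plan's assumptions. The case for acting is that analysis should match design, that the change is cheap, and that adding center after seeing the data would look data-driven.

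**What to change.** In Section 10b, pre-specify the primary model as arm, age group and treatment center. Enter center either as a random intercept or as fixed effects with a pre-stated rule for pooling small centers (for example, centers with fewer than 10 patients form one level). Choose one option now, and use the same center term in the age-by-arm interaction model.

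The cost is SAP wording and a few degrees of freedom. If center has no effect and many small centers are entered as fixed effects, the loss of precision is up to about 1%; the pooling rule or the random intercept is meant to limit this. No change to sample size, data collection or randomization is needed.

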In addition to age stratification (see 10a and 10b), heterogeneity or variation in outcomes will be examined based on pre-specified patient, cancer and treatment-related attributes (“**Table: Pre-specified attributes to examine heterogeneity/patient subgroups**”). These factors are included because they may have an independent association with the outcomes examined. As shown in the power considerations for Objective 1, with our sample size we will have a sufficient power to detect heterogeneity of treatment effect. We will not adjust for the multiplicity of the statistical testing, because the goal of the HTE analyses is not to confirm a specific treatment heterogeneity hypothesis, but to generate hypotheses of potential treatment

heterogeneity. Towards this end, we will focus more on describing the estimated treatment differences in each of pre-specified subgroups than testing.

We have also planned analyses to identify subgroups of patients in which the treatment effect (benefit of short-course therapy) is potentially more pronounced than the average treatment effect, using a multivariable scoring approach.⁵⁵ Specifically, we will derive a multivariable model that predicts the treatment difference for each patient. Based on the predicted treatment difference scores, we will be able to define subgroups or clusters of patients who benefit more from short-course radiation therapy than the average patient on the study. For example, we will make two subgroups: one which consists of patients only with positive predicted treatment differences, and the other which consists of the remaining patients with negative predicted treatment difference. We will estimate the average treatment difference in each of the two subgroups and also perform a test for interaction.

Table: Pre-specified attributes to examine heterogeneity/patient subgroups	
Patient attributes:	Age (younger than 45, 45 and above) Smoking status Body mass index Comorbidity (hypertension, diabetes) Mastectomy specimen weight
Cancer attributes:	Tumor type (ductal, lobular, mixed histology) Tumor size Receptor status Tumor grade
Treatment attributes:	Number of nodes removed Expander versus permanent implant Volume of implant/expander fill Chemotherapy (yes/no) and regimen and timing of chemo Hormonal therapy Radiation therapy fields Bolus regimen Use of acellular dermal matrix Mastectomy scar location Use of biologic therapy

10f. AE Monitoring

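### The SD of change in the PWB power calculation omits a square root, so the age-interaction power is overstated, and two power figures in the text contradict the plan's own table

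*Combined protocol and SAP*

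**What the plan says.** Section 10b (statistical analysis of the primary endpoint and power) expects "the mean post-conventional (long-course) PWB score to be 19.0 for the younger patient group and 24.0 for the older group". It puts the SD at 6.0 in each of the two age groups: "the older group, and that the standard deviation (SD) is 6.0 for each". It then takes a correlation of 0.65-0.70 between the baseline and 6-month scores and concludes "thus the SD of change from baseline to 6 months will be 3.6 to 4.2".

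For 400 patients, a two-sided 0.05 level, a marginal difference of 2.8 points and an SD of change of 4.0, the text says that "power will be 93" percent.

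The power table that follows assumes differences of 4.0 points (younger) and 2.0 points (older). For SDs of change of 3.5, 4.0 and 4.5 it gives main-analysis power >0.99 in every row and interaction power of 0.80, 0.69 and 0.59. The sentence introducing it says the table "reveals the power to detect an age interaction will be 59%-89" percent. The same paragraph calls the estimates conservative, "given that patients in our survey were interviewed between 6 and 24 months".

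Section 10e refers back to these calculations and states that "with our sample size we will have a sufficient power to detect heterogeneity of treatment effect". It also says that "the goal of the HTE analyses is not to confirm a specific treatment heterogeneity hypothesis, but to generate hypotheses of potential treatment" heterogeneity.

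**The concern.** The SD of change is presented as following from the SD and the correlation, but it does not follow by the usual variance formula. Too small an SD inflates every power figure that depends on it. The main comparison has power to spare. The age interaction does not: age is a stratification factor, section 10b commits to testing the interaction, and section 10e relies on these figures to call the study adequately powered for heterogeneity. A reader told that power reaches 89% could take a null interaction test as evidence that the effect is the same in both age groups, when the test may have only an even chance of detecting the difference the plan expects.

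The text and the table also give different power for the same SD, N and effect, so at least one figure in each pair must be wrong.

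**Working it through.** **Inputs from the plan.** Post-treatment SD 6.0 (long-course arm, each age group); ρ = 0.65-0.70; 200 patients per arm; two-sided α = 0.05; expected differences 4.0 and 2.0, so the interaction is 2.0 points; marginal difference 2.8 (all section 10b). The younger share is 40% (section 10a), giving 80 younger and 120 older per arm. Dropout at 6 months is at most 5% (section 10b).

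**Not given in the plan.** The baseline SD and the short-course SD. Values for these are assumptions here, and ρ is taken to apply within each arm and age group.

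**1. Reproducing the stated SD.**
- 6 × 2(1 − 0.70) = 6 × 0.60 = 3.6
- 6 × 2(1 − 0.65) = 6 × 0.70 = 4.2

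Both endpoints match exactly, without the root.

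**2. Correct formula.** With baseline SD b and post-treatment SD p, the SD of change is √(p² + b² − 2ρpb). With p = b = 6 this is 6√(2(1 − ρ)):
- ρ = 0.70: 6√0.60 = 4.65
- ρ = 0.65: 6√0.70 = 5.02

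Under the same equal-SD assumption, the correlation needed for a given SD is 1 − SD²/72. The table rows 3.5, 4.0 and 4.5 need ρ = 0.83, 0.78 and 0.72; the stated 3.6 and 4.2 need 0.82 and 0.755. All lie above 0.65-0.70.

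**3. Could another baseline SD rescue 3.6-4.2?** With p = 6 the expression is smallest at b = 6ρ, where it equals 6√(1 − ρ²) = 4.28 (ρ = 0.70) to 4.56 (ρ = 0.65). So in the long-course arm, where 6.0 is stated, no baseline SD reaches the stated range. For the pooled value this floor holds only if the short-course SD is also 6.0.

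**4. Reproducing the table's interaction power.** SE = √((SD_long² + SD_short²)(1/80 + 1/120)); power = Φ(2.0/SE − 1.96).

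| SD of change (both arms) | SE | Power | Plan's table |
|---|---|---|---|
| 3.5 | 0.714 | 0.799 | 0.80 |
| 4.0 | 0.816 | 0.688 | 0.69 |
| 4.5 | 0.919 | 0.586 | 0.59 |
| 3.6 (stated) | 0.735 | 0.777 | – |
| 4.2 (stated) | 0.857 | 0.645 | – |
| 4.65 (corrected) | 0.949 | 0.559 | – |
| 5.02 (corrected) | 1.025 | 0.497 | – |

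The table is right for its own SDs. With 5% missing (76 and 114 per arm), the last two rows become 0.538 and 0.477. The interaction detectable with 80% power is 2.80 × SE = 2.66-2.87 points.

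**5. Sensitivity to the unstated SDs.** Long-course SD fixed at 6.0; the other SDs are assumed. Ranges run from ρ = 0.70 to 0.65.

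| Baseline SD / short-course SD | Pooled SD of change | Interaction power |
|---|---|---|
| 6.0 / 6.0 | 4.65-5.02 | 0.56-0.50 |
| 6.0 / 5.0 | 4.51-4.86 | 0.58-0.52 |
| 6.0 / 7.0 | 4.89-5.27 | 0.52-0.46 |
| 6.5 / 6.0 | 4.86-5.25 | 0.52-0.46 |
| 5.0 / 6.0 | 4.36-4.69 | 0.61-0.55 |
| 5.0 / 5.0 | 4.12-4.44 | 0.66-0.60 |
| 4.2 / 5.0 | 3.97-4.26 | 0.69-0.63 |

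Main-effect power for 2.8 points is above 0.999 in every row.

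**6. Text against table.**
- *93% at SD 4.0.* 2.8/(4.0 × √(2/200)) = 7.0 standard errors, so power is above 0.9999, in line with the table's >0.99. With 200 per arm, 93% would correspond to a difference of about 1.37 points at SD 4.0, or to an SD of about 8.1 for 2.8 points.
- *Up to 89%.* The table's highest interaction power is 0.80. Reaching 0.89 with 400 patients needs an SD of change of about 3.07, which appears nowhere in the plan. It may be a slip for 80%.

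**The case against.** The strongest reply concerns weight. Section 10e treats the heterogeneity analyses as hypothesis-generating and more descriptive than testing, and the sample size, primary test and decision rule do not depend on the SD of change. The table already extends to SD 4.5 and shows interaction power of 0.59, so against its worst row the correction moves power only to 0.56-0.50. The 93% understates power and so misleads nobody about the adequacy of the main test.

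The replacement range also rests on SDs the plan does not give, and some assumed combinations fall inside the table. The 6.0 itself comes from interviews at 6 to 24 months; with 5.0 throughout (another assumption), the SD of change would be 5√0.60 to 5√0.70 = 3.87-4.18 and power 0.72-0.65.

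All of this stands as a limit on consequence and on the replacement numbers. It does not rescue the derivation: the plan adopts 6.0 as its planning value, and from that value 3.6-4.2 cannot be reached in the long-course arm with any baseline SD. Nor does it remove the two disagreements between text and table. The availability of 0.69 and 0.59 in the table weakens the section 10e claim further rather than defending it.

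**Conclusion.** The point holds as an arithmetic error that should be corrected. The stated SD of change omits a square root. With SD 6.0 at baseline and in both arms it is 4.65-5.02, and power for the 2.0-point age interaction falls from 0.78-0.65 (at the stated SDs) to 0.56-0.50, or 0.54-0.48 with 5% missing. Across the other SD combinations in the sensitivity table, interaction power runs from 0.46 to 0.69. The section 10e statement of adequate power for heterogeneity is therefore not supported by the figures it cites.

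The 93% and 89% contradict the table whatever SDs are assumed. The consequence is confined to the age interaction and the sentences that rely on it.

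**What to change.** - **Section 10b, SD of change:** replace 3.6-4.2 with 4.65-5.02, labelled as assuming SD 6.0 at baseline and in both arms. Alternatively, report the survey's SDs, note the 6 to 24 month interview window, and recompute.
- **Section 10b, main power:** replace 93% with >99%.
- **Section 10b, power table and its introduction:** add rows at SD 4.65 and 5.02 (main >0.99; interaction 0.56 and 0.50). Make the text range match the table: 50%-80% if the existing rows stay, saying that 50%-56% is the range under the equal-SD assumption.
- **Section 10e:** replace the adequate-power sentence with a statement that, assuming SD 6.0 at baseline and in both arms, the age interaction detectable with 80% power is about 2.7-2.9 points. This fits the section's hypothesis-generating purpose. It speaks only to age; no power is shown for the other listed attributes.

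The cost is wording and two table rows, plus a less favourable stated interaction power. No change to the sample size, the test or data collection is needed.
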